9.3 POPULATIONS FOR ANALYSES

All efficacy and safety data summaries and analyses will be performed by study arm using an Intent-to-Treat (ITT) population defined as all randomized patients. The number of patients identified as candidates for the study will be reported, as will the number consented. The number and percentage of patients randomized, patient population (ITT), and treatment status (completed, discontinued/withdrew) will be summarized both by treatment group and overall. Reasons for discontinuation/withdrawal will be presented. An exploratory, per protocol (PP) analysis will focus on patients who used the assigned intervention on at least 50% of days during the first 30-day period.

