6 STUDY INTERVENTION

6.1 STUDY INTERVENTION(S) ADMINISTRATION

6.1.1 STUDY INTERVENTION DESCRIPTION

The two active interventions evaluated in this study are EaseVRx and PainTRAINER. EaseVRx is delivered via a commercially available VR headset. PainTRAINER consists of 2-D visualizations delivered via smartphone or computer.

Skills-Based VR: EaseVRx

EaseVRx was developed by AppliedVR in partnership with pain psychologist [name], Associate Professor of Anesthesiology, Perioperative and Pain Medicine at Stanford University and an NIH- and PCORI-funded investigator in the use of VR for pain management. EaseVRx incorporates the evidence-based principles of CBT, mindful meditation, and physiologic biofeedback therapy using embedded biometric sensors. It combines psychoeducation, pain education, breathing training, relaxation exercises, and executive functioning games to provide a mind-body approach toward living better with chronic pain. The standardized, prescriptive, and reproducible 56-day program delivers a combination of skills training and CBT-related treatments through scheduled daily virtual experiences. The participants are allowed to complete as many sessions as they would like. In addition to the prescribed schedule of content the participant will have access to the full library of content. Each VR experience lasts between 2-16 minutes, with an average duration of 6 minutes. The VR treatment modules are designed to minimize triggers of emotional distress or cybersickness. There are 5 types of modules:

- **Interoceptive:** These modules are designed to help the user understand and perceive what is happening inside the body. They provide a biofeedback-like platform in which the changes in the observed environment reflect a progressively enhanced state of relaxation.
- **Education:** Help the user understand why the VR exercises are relevant to their pain, as well as teaching specific topics often used in pain psychology, including the neurobiology of pain, the role of mood and stress in pain, pain catastrophizing, activity pacing and setting goals. The goal is for the user to create self-management steps and a toolkit of strategies they can use to manage their response to pain.
- **360-degree videos:** High-quality 360 videos with voiceovers, music, and sound effects that are designed to maximize relaxation and engagement of users.

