PainTRAINER includes eight 35-45 minute sessions; each teaches an evidence-based pain coping skill. Users complete one session per week in a predetermined order and can close a session before completing it and later resume where they left off. They can also review completed sessions (e.g., an audio recording of a skill practice, or instructions on how to use a skill). **The program uses an adaptive, mobile responsive mHealth platform:** Users can access it with any Internet-enabled tablet, personal computer, or smartphone. **Smartphone access is important; these devices are increasingly the main platform used to access the Internet, including in underserved populations.** During development of *PainTRAINER*, patients clearly advocated for access to program content and resources through smartphones. Training is led by a

computerized virtual coach who speaks to users. **Content is provided in audio to minimize reading and facilitate program completion for sick or low literacy patients.** Important information is highlighted on screen with brief, large-font text, with photos, graphics, animations, and interactive exercises to reinforce learning. We also added other features to enhance learning and mastery of skills, guided by *social cognitive theory* (e.g., social modeling), *adult learning theory* (e.g., tying skills to personal goals and experiences), *principles of multimedia instruction* (interactive exercises, graphics to reinforce explanations), and *behavior change theory* (e.g., behavior tracking, reminders).

The program includes: (i) the Home Page (customized to users' progress and status by the expert system); (ii) Training Sessions; and (iii) the Expert System (a knowledge database and programmed decision rules or "algorithms" that customize users' experience based on their progress in the program). A login screen takes users to the home page where they access the current week's session, which is highlighted. From there, users access program sessions and features that allow them to manage reminders and goals, log practices, and review progress in easy-to-read graphs. **The interface applies accepted principles of user-centered design to enhance usability in diverse**

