populations (e.g., screen layout consistent with major websites; use of audio to minimize reading; simple menus placed predictably on-screen; clear and consistent navigation aids; direct access to important screens and help). **Screen elements are designed for a diverse population** (e.g., easy-to-read type, plain language and audio for low literacy users, images of people from diverse race/ethnic backgrounds). Written content follows federal guidelines for plain language to ensure it is easy to read, understand, and use. The program's back-end database tracks program use meta-data, including sessions experienced, time spent on session, and time of day the session was reviewed. These meta-data allow for secondary "dose-response" analyses. **Figure 1** shows the home page.

Figure 1: PainTRAINER home page

PainTRAINER has been validated in clinical trials, including multiple RCTs. Bennell et al. studied the program in a participant-blinded trial of patients with chronic pain and found greater increases in function, pain coping, and global improvement than a control condition after eight weeks; benefits persisted at 52 weeks and 91% of participants (older adults, **largely from rural, low income areas, consistent with the current study population**) completed all 8 sessions.⁴⁷ Rini et al. found similar results in a controlled trial in patients with painful arthritis that demonstrated improved self-efficacy, reduced anxiety, and less pain-related interference with functioning.⁴⁸ Qualitative research reveals that patients find the program easy to use and are likely to recommend the app to others.⁵⁰ Taken together, research indicates that *PainTRAINER* as an effective and acceptable mHealth app that can reduce pain and psychological disability and has proven acceptable to users in rural communities. These findings are consistent with a Cochrane meta-analysis of RCTs of web-based behavioral interventions for persistent pain that found improvements in pain, impairment, depression, and anxiety.⁵⁵

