6.1.2 DOSING AND ADMINISTRATION

All participants are instructed to use the VR program at least once a day and as needed throughout the 8 week study period. Thereafter, the participant can use the program as needed. Section 4.3 provides the justification of dose. PainTRAINER delivers eight sessions via any web-connected platform,

including Android or iOS smartphones, tablets, or personal computers. Patients will complete one session per week in a pre-determined order.

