7.2 PARTICIPANT DISCONTINUATION/WITHDRAWAL FROM THE STUDY

Participants are free to withdraw from the study at any time upon request. Participants who request to withdraw will be given the option to continue completing the periodic survey questionnaires, if they choose to continue responding to surveys, they will not be withdrawn. An investigator may withdraw a participant who develops any of the exclusions criteria in section 5. the

The reason for participant discontinuation or withdrawal from the study will be recorded. Subjects who signed the informed consent form, were randomized and received the study intervention, and subsequently withdraw, or are withdrawn from the study without engaging with the study intervention (defined as any recorded VR or painTRAINER metadata by participant or self-reported usage of intervention in survey responses) will be replaced.

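### The exploratory per-protocol rule (use on 15 of 30 days) is half the EaseVRx schedule but, at one day per session, 3.0 to 3.75 times the PainTRAINER schedule

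*Combined protocol and SAP*

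**What the plan says.** Section 9.3 makes intention-to-treat the main population: "All efficacy and safety data summaries and analyses will be performed by study arm using an Intent-to-Treat (ITT) population". It then adds one further set: "exploratory, per protocol (PP) analysis will focus on patients who used the assigned intervention on at least 50% of days during the first 30-day" window. The same calendar-day rule serves both arms, and 9.3 does not say what counts as a day of use.

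Section 6.1.2 gives the two schedules. For EaseVRx: "All participants are instructed to use the VR program at least once a day". For PainTRAINER: "Patients will complete one session per week in a pre-determined order". Section 6.1.1 puts the PainTRAINER total at eight sessions.

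Both programs allow use beyond the schedule (6.1.1). For EaseVRx, "The participants are allowed to complete as many sessions as they would like". PainTRAINER sessions can be paused and resumed, finished sessions can be revisited, and users have "features that allow them to manage reminders and goals, log practices, and review progress in easy-to-read graphs". No frequency is set for any of this.

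The nearest definition of use is in 7.2, where engagement is "defined as any recorded VR or painTRAINER metadata by participant or self-reported usage of intervention in survey responses". It was written to decide which withdrawn participants are replaced, not who enters the per-protocol set.

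**The concern.** A per-protocol set is meant to hold the patients who followed their assigned schedule well enough. Here one day count is laid over a daily program and a weekly one. Doing exactly what PainTRAINER asks does not place a patient in the set, while doing half of what EaseVRx asks does.

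The EaseVRx set would therefore include partial adherers. The PainTRAINER set would hold only patients whose use went well beyond the weekly schedule, who may differ in motivation, time or symptoms. A between-arm contrast in these sets mixes the treatment difference with a difference in how strictly each arm was filtered. Because use is undefined, the analyst must also decide whether a login, a practice log or a half-finished session counts, and that decision could determine who makes up the PainTRAINER set.

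**Working it through.** **Inputs**

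- Threshold: 50% of the first 30 days (9.3).
- EaseVRx schedule: at least once a day, so 30 scheduled days in 30 (6.1.2).
- PainTRAINER schedule: one session per week (6.1.2), eight in all (6.1.1).
- Assumption for the base case: one PainTRAINER session takes one use-day.

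The 50% rule is a choice, not a derived figure, so there is no stated result to reproduce.

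**Step 1. Threshold in days.** 0.50 × 30 = 15 days, in both arms.

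**Step 2. Weekly sessions in a 30-day window.** If the first session falls on day 1 or 2, sessions also fall 7, 14, 21 and 28 days later, which gives 5. If it falls on days 3 to 7, there are 4.

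**Step 3. Threshold relative to schedule.**

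| Arm | Scheduled use-days in 30 | Share of days at exact adherence | Threshold ÷ schedule |
|---|---|---|---|
| EaseVRx | 30 | 100% | 15/30 = 0.5 |
| PainTRAINER, 5 sessions | 5 | 5/30 = 16.7% | 15/5 = 3.0 |
| PainTRAINER, 4 sessions | 4 | 4/30 = 13.3% | 15/4 = 3.75 |

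Relative to schedule, the PainTRAINER standard is 3.0/0.5 = 6 to 3.75/0.5 = 7.5 times as demanding. Even all eight sessions, done on separate days within the 30, would give only 8/30 = 26.7%.

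**Step 4. Optional use needed to qualify.** A PainTRAINER patient with 4 session-days needs 15 − 4 = 11 further days out of 30 − 4 = 26 (42.3%). With 5 session-days, it is 10 out of 25 (40.0%).

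**Step 5. Illustration only.** Let *p* be the chance of optional use on each non-session day, independent between days. The documents give no value for *p* and no basis for independence, so both are assumptions. The chance of qualifying is P(Bin(26, *p*) ≥ 11) or P(Bin(25, *p*) ≥ 10):

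| *p* | 4 sessions | 5 sessions |
|---|---|---|
| 0.1 | 0.0% | 0.0% |
| 0.2 | 0.8% | 1.7% |
| 0.3 | 12.5% | 18.9% |
| 0.4 | 47.9% | 57.5% |
| 0.5 | 83.7% | 88.5% |

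The spread shows that the make-up of the PainTRAINER set depends on optional behaviour that the plan neither schedules nor says how to count.

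**The case against.** The strongest reply is that nothing important rests on this set. Section 9.3 puts the efficacy and safety analyses on intention-to-treat and labels the per-protocol analysis exploratory, and sections 9.4.2, 9.4.3 and 9.4.7 do not use it. That is correct, and it limits the weight of the point. It does not make the rule right: this is the only adherence-based population in 9.3, and its name would mislead a reader of the results.

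A second reply is that the ratio of 3.0 to 3.75 assumes one day per session. Split sessions, review and practice logging can add use-days, so the PainTRAINER set need not be empty. This also stands. But these activities are optional and unscheduled, so a patient who qualifies through them has gone beyond the schedule, and the asymmetry remains.

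Third, any set selected on use after randomisation loses randomised comparability, whatever the threshold. True; the unequal standard is an added problem, not the only one.

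Fourth, a common count of engagement days could have been intended. Section 9.3 gives no such rationale and calls the set per protocol. Nor are days equal exposure here: section 6.1.1 gives an average of 6 minutes per VR experience and 35 to 45 minutes per PainTRAINER session.

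**Conclusion.** The concern holds. As written, the rule admits an EaseVRx patient at 0.5 of schedule and can exclude a PainTRAINER patient at full schedule, for whom the threshold is 3.0 to 3.75 times the scheduled session-days. The ratios follow from sections 9.3 and 6.1.2 and assume one use-day per session; no other section sets an arm-specific threshold or defines use for this set.

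The documents do not allow the direction or size of any bias to be worked out, nor the number of PainTRAINER patients who would qualify through optional use. The consequence is confined to the exploratory per-protocol analysis. It should be corrected, since a prespecified comparison would otherwise be hard to interpret, but no main conclusion of the trial depends on it.

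**What to change.** Amend section 9.3 before unblinding.

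1. **Define use for this set.** State which recorded event makes a VR use-day, and when a PainTRAINER session that was paused and resumed counts as completed. Say whether the source is program metadata, the weekly Treatment Usage Questionnaire in the schedule of activities (1.3), or both. State also the day on which the 30-day window opens, which 9.3 leaves unsaid.
2. **Use the same proportion of each arm's own schedule over the same window.** For example, at least 50% of scheduled VR days (15 of 30), counted as days and not as experiences because VR sessions are unlimited, and at least 50% of PainTRAINER sessions due: 2 of 4, or 3 of 5 if the first falls on day 1 or 2. These cut-offs are examples for an analysis set and change nothing in how patients use either program.
3. **Optional sensitivity analysis.** A full 8-week version (28 of 56 days; 4 of 8 sessions) could be added. The choice of window is a matter of preference.
4. **Keep the exploratory label**, since the set is still selected after randomisation.

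The cost is a sentence or two and a little programming. The data exist: the PainTRAINER "back-end database tracks program use meta-data, including sessions experienced, time spent on session", and section 8.2.1 has the headset recording the date of use and the module chosen. Conduct, sample size and the intention-to-treat analyses stay as they are.

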9.4 STATISTICAL ANALYSES

9.4.1 GENERAL APPROACH

All statistical analyses will be performed jointly by the Cedars-Sinai Biostatistics Core and the Cedars-Sinai Center for Outcomes Research and Education (CS-CORE) using SAS® software version 9.3 or higher (SAS Institute, Cary, NC, USA), R version 3.5.0 or higher (R Foundation for Statistical Computing, Vienna, Austria) or Stata software version 14 or higher (StataCorp LLC, College Station, TX, USA). Continuous variables will be summarized using descriptive statistics (N, mean, standard deviation, minimum, median, and maximum as appropriate). Categorical variables will be summarized using the number and percentage of patients in each category. Data will be summarized with respect to patient demographic and baseline characteristics both across the study and by study-arm. The efficacy endpoints, safety assessments, and other outcome results for each treatment group will be summarized descriptively unless otherwise indicated. In addition, statistical model estimates of least squares means, treatment differences, p-values and 95% confidence intervals will also be provided where relevant. The fit of general linear models will be assessed using residual plots and/or other diagnostic plots as appropriate. The fit of logistic models will be assessed using Hosmer-Lemeshow goodness-of-fit and/or receiver operating characteristic (ROC) curves as appropriate. All statistical tests will be 2-sided and performed at the 0.05 level of significance unless stated otherwise.

Multiple Comparisons/Multiplicity: The family-wise type I error rate (FWER) for the statistical tests of the primary and secondary endpoints will be controlled at 0.05. To strongly control the FWER at this level, a gatekeeping approach will be utilized. A closed testing procedure will be employed to control the FWER. Any hypothesis tests conducted for model building purposes will be conducted outside of any gatekeeping.

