3 OBJECTIVES AND ENDPOINTS

OBJECTIVES	ENDPOINTS	JUSTIFICATION FOR ENDPOINTS
Primary		
To compare the effectiveness of 3D immersive Skills-Based VR with 2D mobile health application in improving perceived pain intensity from baseline to week 8. The trial will be considered a success if there is statistical evidence of difference in improvement between EaseVRx group and PainTRAINER group.	The change from study baseline to week 8 in daily pain intensity as measured by the standard 11-point numeric rating scale (NRS) with a 24-hour recall is the primary endpoint. The minimally clinically important difference (MCID) on the pain NRS is 2 points.	The NRS response scale is most often recommended in guidance documents. The empirical basis slightly superior measurement properties (e.g., reliability, validity, responsiveness) across a wide variety of contexts compared to other response scales ³⁷ .
Secondary		
To compare the effectiveness of 3D immersive Skills-Based VR with 2D mobile health application in improving pain interference from baseline to Week 8. The trial will be considered a success if there is statistical evidence of difference in improvement between the EaseVRx group and PainTRAINER group.	The change from study baseline to week 8 pain interference as measured by the 8-item PROMIS PI scale is a secondary endpoint. This scale measures the consequences of pain on relevant aspects of life, including the extent to which pain hinders engagement with social, cognitive, emotional, physical, and recreational activities. We will test for a statistically significant difference of 5 points in the PROMIS PI score from baseline, and compare differences between either EaseVRx group and PainTRAINER group.	The PROMIS scale is a validated instrument with excellent content validity, construct validity, and reliability in patients with chronic pain. ³⁸ Past work indicates that changes of 3.5 to 5.5 points in PROMIS-PI scores of people with LBP can be considered meaningful. ³⁹

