To compare the effectiveness of 3D immersive Skills-Based VR with 2D mobile health application in improving perceived self-reported pain catastrophizing from baseline to Week 8. The trial will be considered a success if there is statistical evidence of difference in improvement between EaseVRx group and PainTRAINER group.	The change from study baseline to Week 8 in pain catastrophizing as measured by PCS SF-6 is a secondary endpoint. We will test for a difference in rates of high catastrophizing as defined by a score of ≥ 7 on the PCS-SF6, and compare these differences between EaseVRx group and PainTRAINER group.	The NIH Pain Consortium RTF draft standards for research on cLBP recommend a uniform minimal data set that includes self-report measures of pain catastrophizing. ⁴⁴ Further, changes in catastrophizing are associated with improvement in multidisciplinary pain treatment. ⁴⁵
To compare the effectiveness of 3D immersive Skills-Based VR with 2D mobile health application in reducing use of opioids from baseline to Week 8. The trial will be considered a success if there is statistical evidence of difference in improvement between EaseVRx group and PainTRAINER group.	The change from study baseline to Week 8 in weekly average opioid dosage calculated as a 7-day average of daily maximum milligrams morphine equivalent (MME) is a secondary endpoint. We will test for a greater than .5 SD in change from baseline, and compare differences between EaseVRx group and PainTRAINER group.	Despite some evidence from randomized controlled trials (RCTs) on the efficacy of opioids in the short-term treatment of low back pain, little evidence is available on long term efficacy and safety. Lowering MME as prescribed while lowering pain is an important goal of cLBP treatments. ⁴⁶

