9.2 SAMPLE SIZE DETERMINATION

Sample Size calculations and Power Estimation

Sample Size calculations and Power Estimation

Sample Size Calculation: The primary goal of the study is to test the effectiveness of *PainTRAINER* vs. *EaseVRx*, in reducing pain intensity. The trial will be testing if there is statistical evidence that either *PainTRAINER* or *EaseVRx* is more effective in lowering average weekly pain intensity after 8 weeks from start of intervention. We estimate power to assess the effect of the

Table 1. Minimum detectable odds ratio as a function of the proportion of variability in treatment type that is explained by all other relevant covariates in the model and the baseline probability of positive treatment response.

Baseline probability	R ²			
	0.0	0.1	0.2	0.4
0.2	2.32	2.42	2.55	2.91
0.3	2.17	2.25	2.37	2.69
0.5	2.15	2.25	2.37	2.74

interventions on the treatment response (achievement of a minimally clinically important difference [MCID] of 2.0 on the NRS^{56,57} (y/n)) using logistic regression, accounting for possible confounding factors for the primary outcome described in Aim 1. The dependent variable is the treatment response and the main independent variable of interest is *PainTRAINER* vs. *EaseVRx*. **Table 1** displays the minimum odds ratio that can be detected with 90% power with the two-sided 0.05 level of significance as a function of baseline probability of positive response when a patient is treated with *EaseVRx* and R², the proportion of variability in the predictor of interest that is explained by all relevant baseline covariates in the model using data from 150 patients in the *PainTRAINER* arm and 150 in the *EaseVRx*. For example, data from 300 patients achieve 90% power to detect an odds ratio of 2.25 if the probability of positive response when a patient is treated with *PainTRAINER* is 0.3 and 0.1 of the variability in intervention is explained by all other baseline covariates in the model. These odds ratios vary between 2.15 and 2.91 and are clinically meaningful. Therefore, we have enough power to test statistical significance of predictors in the multivariable logistic regression model. Regarding clinical significance, given an MCID of 2 points on the NRS and a SD of 2 on this scale from our own digital health trials, data from 150 patients in each group

will achieve 90% power to detect a mean pain intensity score difference of 0.75, corresponding to a clinically meaningful effect size of 0.38 SD.

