9.4.2 ANALYSIS OF THE PRIMARY ENDPOINT(S)

Pain Intensity - The goal of this analysis is to test the effectiveness of PainTRAINER vs. EaseVRx in decreasing reported pain intensity. The trial will be a success if there is statistical evidence that either PainTRAINER or EaseVRx is more effective in reducing pain intensity. The primary outcome will be the baseline vs. week 8 difference-in-difference in 7-day average NRS pain intensity scores, dichotomized into if the MCID of 2 is achieved. The between arm difference of achieving the MCID of 2 will be tested using Chi-squared test.

- Additionally, we will use a logistic regression to determine whether the odds of achieving the MCID of 2 is different between the two groups after accounting for baseline-scores by including them as one of the predictors.

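### Section 3 lets any one of five secondary endpoints make the trial a success, which conflicts with Section 9.4.2 and with the gatekeeping that Section 9.4.1 promises but does not specify

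*Combined protocol and SAP*

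**What the plan says.** Three parts of the combined protocol and SAP bear on what counts as success.

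- **Section 3 (Objectives and Endpoints).** The pain interference and anxiety rows each state: "The trial will be considered a success if there is statistical evidence of difference in improvement between the EaseVRx group and PainTRAINER group". The self-efficacy, catastrophizing and opioid rows carry the same sentence with trivial differences: "The trial will be considered a success if there is statistical evidence of difference in improvement between EaseVRx group and PainTRAINER group". The primary row has it too. None of the five secondary rows makes it conditional on the primary result.
- **Section 9.4.2.** For pain intensity: "The trial will be a success if there is statistical evidence that either PainTRAINER or EaseVRx is more effective in reducing pain intensity".
- **Section 9.4.1.** "The family-wise type I error rate (FWER) for the statistical tests of the primary and secondary endpoints will be controlled at 0.05". It continues: "To strongly control the FWER at this level, a gatekeeping approach will be utilized", and then "A closed testing procedure will be employed to control the FWER". It does not say which hypothesis comes first, in what order the others follow, how alpha is divided, or which intersection tests the closed procedure uses. The only per-test level given is the general two-sided 0.05.

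Sections 8.1, 9.1 and 9.4.3 list the secondaries in one order: interference, catastrophizing, anxiety, self-efficacy, MME (ignoring a repeated interference entry in 8.1). The two lists in the synopsis, Section 3 and Section 4.1 use four other orders. None is called a testing sequence.

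**The concern.** Gatekeeping on the primary exists to stop a trial that misses its primary endpoint from being declared positive on something else. Section 3 as worded permits exactly that: with no significant difference in pain intensity, one significant secondary out of five is enough. Section 9.4.1 could settle the matter, but gatekeeping and closed testing are classes of procedure. Until the order and levels are written down, the promised control can be neither carried out nor checked from the text. The headline conclusion of the trial could then depend on which section is followed, and the order of the secondaries could be chosen after the data are seen.

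**Working it through.** **The plan's own figures.** The stated family-wise rate of 0.05 cannot be reproduced, because the procedure that would deliver it is not defined. The design power in Section 9.2 can: 150 per arm, difference 0.75, SD 2 gives 0.75 / (2 × √(2/150)) = 3.248, and Φ(3.248 − 1.960) = 0.901, against the stated 90%.

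**Inputs.** Six routes to success (one primary, five secondaries) from Section 3. Two-sided 0.05 per test from Section 9.4.1. The documents give no correlations between endpoints, so I assume equal correlation ρ among the six test statistics and show 0, 0.3, 0.5 and 0.7.

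**Section 3 taken literally, all nulls true.** Under independence:

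- any false success: 1 − 0.95^6 = 0.265
- from a secondary, with the primary not significant: 0.95 × (1 − 0.95^5) = 0.215

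For ρ > 0, let g(u) be the probability that one test does not reject, given the shared normal factor u. Any false success is 1 − E[g(U)^6]. Because E[g(U)] = 0.95, the secondary-only part is that value minus 0.05.

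| ρ | Any of six | Secondary only, primary not significant | Success on primary alone |
|---|---|---|---|
| 0 | 0.265 | 0.215 | 0.05 |
| 0.3 | 0.241 | 0.191 | 0.05 |
| 0.5 | 0.207 | 0.157 | 0.05 |
| 0.7 | 0.164 | 0.114 | 0.05 |

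The secondary-only share of false successes runs from 0.215/0.265 = 81% to 0.114/0.164 = 70%.

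**Why a primary-first rule alone is not enough.** This is a different scenario and should not be compared with the table above: the primary effect is real with 90% power (shift 1.960 + 1.282 = 3.242) and all five secondaries are null. The chance of at least one false secondary claim at ρ = 0 / 0.3 / 0.5 / 0.7 is:

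- each secondary at 0.05 once the primary passes: 0.204 / 0.181 / 0.147 / 0.105 (at ρ = 0, 0.9 × (1 − 0.95^5))
- Holm over the five: 0.044 / 0.039 / 0.031 / 0.021 (at ρ = 0, 0.9 × (1 − 0.99^5))
- fixed sequence, each at 0.05: 0.045 / 0.043 / 0.039 / 0.033 (at ρ = 0, 0.9 × 0.05)

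Strong control, which Section 9.4.1 promises, rules out the first option. Either of the others honours the promise, but the text does not say which is meant. With all six nulls true, the fixed sequence has a family-wise rate of 0.05 whatever the correlation, because nothing can be claimed unless the primary rejects.

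**The case against.** The strongest reply is that Section 9.4.1 governs. Section 3 speaks only of statistical evidence and sets no level, test or waiver; Section 9.4.1 covers primary and secondary endpoints by name and commits to strong control. Read together, a secondary supplies statistical evidence only through that procedure, and the Section 3 sentences are repeated table wording. Much of this stands. It is why 0.265 cannot be called the plan's error rate. It does not remove the point: no passage gives Section 9.4.1 precedence, the sentences say the trial succeeds and not merely that objective, and the procedure that would do the overriding is not written out.

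Some stronger readings are tempting, and the documents do not support them.

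- *Sections 3 and 9.4.2 strictly contradict each other.* Section 9.4.2 says *if*, not *only if*. They are inconsistent, not logically incompatible.
- *The plan leaves the deciding test open everywhere.* For the primary, "The between arm difference of achieving the MCID of 2 will be tested using Chi-squared test", with logistic regression added. For the four patient-reported outcomes the t-test comes first and ANCOVA is additional. For MME, ANCOVA is the named analysis. The ordinary reading is a main test with supportive analyses, although the plan does not say that these are the tests entering the multiplicity procedure.
- *The primary test should become logistic regression because it is what was powered.* Section 9.2 does say "Therefore, we have enough power to test statistical significance of predictors in the multivariable logistic regression model", but that model adjusts for all relevant baseline covariates, whereas the one in Section 9.4.2 adds only the baseline score. Section 9.2 also powers a mean difference. A change of test is a separate choice that this defect does not require.
- *The family of hypotheses is undefined.* The Coronavirus anxiety wording in Sections 9.1 and 9.4.3 and the pain interference label on the primary in Section 9.1 look like leftovers. The Section 9.1 outcome line for anxiety itself names the PROMIS scale, as do the synopsis, Section 3 and Section 8.1.

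**Conclusion.** The point holds as an inconsistency that should be removed before unblinding. Five sentences in Section 3 award trial success on a secondary endpoint alone, against the success rule in Section 9.4.2 and the family-wise promise in Section 9.4.1, and Section 9.4.1 is too incomplete to resolve it. Applied literally, Section 3 would raise the chance of a false trial success from 0.05 to between 0.164 and 0.265, most of it from trials whose primary was not significant. That range assumes all six nulls true, each test at two-sided 0.05, and equal correlations from 0 to 0.7 that the documents do not supply. A reader might infer that the trial as planned runs at that error rate. It does not follow: Section 9.4.1 read as governing excludes it, so inflation is possible, not demonstrated.

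**What to change.** 1. **Section 3.** Delete the success sentence from the five secondary rows, or reword it as success on that objective subject to Section 9.4.1. Trial success then rests on pain intensity, as in Section 9.4.2.
2. **Section 9.4.1.** State that the primary is tested first at two-sided 0.05 and that the five secondaries are tested only if it is significant, in the fixed order of Sections 9.1 and 9.4.3 (interference, catastrophizing, anxiety, self-efficacy, MME), each at 0.05 and stopping at the first failure. Holm at family-wise 0.05 over the five is an acceptable alternative.
3. **One test per endpoint.** State which test enters the procedure. By default take the one the plan names first: chi-squared for the primary, the t-test for the four patient-reported outcomes, ANCOVA for MME. All other analyses are supportive. Moving to the adjusted models is optional and not part of this point.
4. **Clerical.** Tidy the anxiety wording in Sections 9.1 and 9.4.3 and the primary label in Section 9.1.

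**Cost.** N = 300 and the primary alpha are unchanged. Secondaries after a failed step become descriptive. In a fixed sequence the last endpoint pays most: if all six tests had 90% power and were independent, it would be claimed with probability 0.9^6 = 0.53.

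Holm's first step is at 0.05/5 = 0.01. For an effect with 90% t-test power at 0.05, t-test power there is Φ(3.242 − 2.576) = 0.747. ANCOVA power is Φ(3.242/√((1+r)/2) − z), where r is the baseline to Week 8 correlation (assumed 0.3 / 0.5 / 0.7). It falls from 0.980 / 0.963 / 0.940 with z = 1.960 to 0.926 / 0.878 / 0.826 with z = 2.576. These Holm figures are before allowing for the chance that the primary fails.
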